### **2.3. Descriptive Outcomes**

Descriptive data will be registered at baseline: age, sex, height, weight, body mass, pre-injury work and physical activity status (ATRS, IPAQ, WPAI:GH), cause of injury, health status.

### **2.4. Specification of endpoints**

The primary outcome ATRS will be measured at the primary endpoint 13 weeks.

## 3. Study Design

This study is designed as a randomised controlled superiority trial.

### 3.1. Sample Size

Sample size calculations is based on the primary endpoint ATRS with a clinical relevant difference at 10 points and estimated standard deviation 15 point(19,20). With a two-sided 5% significance level and a power of 80%, the sample size will be 37 in each group and a total of 82 patients when allowing for potential dropouts.

### 3.2. Randomization and Blinding

The randomization procedure:

The participants will be allocated to two groups in a 1:1 randomization using a computer-generated sequence on [www.sealedenvelope.com](http://www.sealedenvelope.com). A staff member with no connection to the project will be responsible for generation of the randomization key and numbered sealed opaque envelopes.

The randomization will be Permuted Block Randomization in block sizes of 2, 4 and 6 with stratification for hospital allocation to allow for minor differences in the treatment (the intervention will be the exact same at the two places, but there could be minor differences in treatment procedure) due to different logistic/culture at the two hospitals. As there is a male to female ratio of 3-5:1 sex is also added to the stratification.

Blinding procedure:

The participants and the physiotherapist supervising the exercise sessions cannot be blinded. The physiotherapist performing the outcome assessment at follow-up will be blinded to the group allocation. The assessor will not be involved in the intervention or be affiliated with the treatment sites. Participants are asked to keep the group allocation secret from assessor. The principal investigator and the statistician performing the statistical analysis will be blinded.

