## Methods: Assignment of Interventions (for controlled trials)

### Allocation

#### 16a Sequence generation

Randomization of participants is performed using a random number generator on [www.sealedenvelope.com](http://www.sealedenvelope.com) and it will be stratified by sex, as female sex is less present and is associated with lower outcome in the ATRS. Block randomized in random concealed block sizes of 2-4 (1:1) into two parallel groups is used to avoid imbalance in the randomization between the intervention groups.

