## **20. Statistical methods**

### **20a Statistical methods for analysing primary and secondary outcomes**

The primary intention-to-treat analysis will investigate the between-group difference in ATRS. We will use a linear mixed effects regression model with the participant as random effect and time 13, 26 and 52 weeks, group allocation (standard care vs standard care plus add-on) and baseline value as fixed effects. Conclusions will only be drawn based on the primary endpoint (13 weeks).

All statistical analyses will be performed by a blinded data analyst according to a pre-established analysis plan. This plan is written in consultation with a statistician and will be published on the Aalborg University website before the inclusion of the last participant. STATA will be used as statistical software. We will use Q-Q plots and histograms to assess data normality.

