### ***6.1. Primary Endpoint***

Descriptive statistics (mean (standard deviation) or median (interquartile range) for continuous variable or frequencies and proportions for categorical variables) will be used to describe demographics, for the two treatment groups individually and overall sample.

The primary intention-to-treat analysis will investigate the between-group difference in ATRS. We will use a linear mixed effects regression model with the participant as random effect and time 13, 26 and 52 weeks, group allocation (standard care vs standard care plus add-on) and baseline value as fixed effects. Conclusions will only be drawn based on the primary endpoint (13 weeks). We will use Q-Q plots and histograms to assess data normality.

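### The primary model leaves out the randomisation strata, and the protocol and SAP disagree on what those strata and block sizes are

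*SAP*

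**What the plan says.** **Allocation, protocol 16a.** Randomisation is "stratified by sex, as female sex is less present and is associated with lower outcome in the ATRS", using "random concealed block sizes of 2-4 (1:1) into two parallel groups". Hospital is not a stratum, although protocol section 8 describes a two-centre trial.

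**Allocation, SAP 3.2.** "The randomization will be Permuted Block Randomization in block sizes of 2, 4 and 6 with stratification for hospital allocation". The reason given for hospital is that "the intervention will be the exact same at the two places, but there could be minor differences in treatment procedure". Sex follows: "As there is a male to female ratio of 3-5:1 sex is also added to the stratification".

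**Primary model.** Protocol 20a specifies a random effect for each participant. Its other terms are: "time 13, 26 and 52 weeks, group allocation (standard care vs standard care plus add-on) and baseline value as fixed effects". SAP 6.1 repeats this, ending in "group allocation (standard care vs standard care plus add-on) and baseline value as fixed effects". Neither sentence contains sex or hospital. Protocol 20b answers N/A for adjusted analyses, and SAP section 6 adds none.

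**The concern.** There are two linked problems.

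First, a reader cannot tell from these documents how patients were allocated. Each document gives reasons for its own strata. Neither explains why the schemes differ or which one produced the list, and the allocation method has to be reported correctly.

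Second, the analysis does not follow the design. Stratifying on sex balances it between the arms. If sex predicts ATRS, as the protocol says, leaving it out of the model returns that balanced variation to the residual. The model-based standard error is then larger than the true sampling error of the treatment difference. What is at stake is precision and power at the single endpoint from which conclusions will be drawn. Validity is not threatened, because the error is in the conservative direction.

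**Working it through.** **1. The schemes side by side**

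| | Protocol 16a | SAP 3.2 |
|---|---|---|
| Strata | sex (2 strata) | hospital and sex (4 strata) |
| Block sizes | 2-4 (with 1:1 allocation, 2 and 4) | 2, 4 and 6 |
| In the primary model | no | neither factor |

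Both documents agree on sex, 1:1 allocation, the web-based generator and sealed opaque envelopes. They differ on the hospital stratum and on block size 6.

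**2. The plan's own sample size.** The inputs from protocol section 14 and SAP 3.1 are a difference of 10, SD 15, two-sided 5% and 80% power. The two-sample t-test needs 36.31, rounded up to 37 per group, as stated. Power at 37 per group is 80.8%. The 82 randomised against 74 analysed implies 1 - 74/82 = 9.8% dropout.

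**3. Assumptions.** The documents give no ATRS difference by sex or hospital.
- Share of women p: a 3-5:1 ratio gives 1/6 to 1/4, or 17-25%. I use 20%. Among 82 patients that range is about 14 to 21 women.
- SD 15 is taken as the total SD across sexes.
- The sex gap is varied over 0, 5, 10 and 15 points.
- The comparison is at 13 weeks only, without the baseline covariate.

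**4. Closed form.** The share of variance explained by sex is R² = p(1-p) × gap² / 15². The excess interval width when sex is omitted is 1/√(1-R²) - 1. For a gap of 10: R² = 0.16 × 100/225 = 0.071, and 1/√0.929 - 1 = 3.8%.

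**5. Simulation.** There were 10,000 trials per setting, with 82 randomised under each scheme, 8 random dropouts, no treatment effect and no hospital effect. For the SAP scheme, 30% of patients were assumed to be at the second hospital. Each trial was analysed by linear regression with and without sex. Monte Carlo error on the type I error is about 0.2 points.

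| Sex gap | R² | Excess width, formula | Excess width, simulated | Type I error without sex (protocol / SAP scheme) | Power with sex, 37 per group |
|---|---|---|---|---|---|
| 0 | 0 | 0% | about 0% | 5.2 / 5.1% | less than 0.1 point below 80.8% |
| 5 | 0.018 | 0.9% | 0.8% | 4.9 / 4.6% | 81.4% |
| 10 | 0.071 | 3.8% | 3.6% | 4.3 / 4.6% | 83.5% |
| 15 | 0.160 | 9.1% | 9.0% | 3.5 / 3.6% | 87.0% |

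Over 17-25% women, the simulated excess is 0.7-0.9%, 3.2-4.4% and 7.9-10.9% for gaps of 5, 10 and 15. The mean estimate stayed within 0.1 point of zero in every setting, so there is no bias.

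In ATRS points at a gap of 10, the width without sex is 2 × 1.993 × 15 × √(2/37) = 13.9. With sex, the SD is 15 × √0.929 = 14.46 and the width is 13.4.

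The power column uses a noncentral t with SD 15√(1-R²) and 71 degrees of freedom. Setting it against the nominal 80.8% slightly overstates the gain, because balance on sex by itself raises the power of the unadjusted test. In a separate simulation (6,000 runs, protocol scheme, sex gap 10, plus a 5-point hospital effect), power was 82% without sex and 84% with it.

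**6. Baseline ATRS in the model.** If the recalled pre-rupture score absorbs a share a of the sex variance, the excess is 1/√(1 - R²(1-a)/(1-R²a)) - 1. With a = 0.5 this is 0.5%, 1.9% and 4.7% for gaps of 5, 10 and 15. With a = 1 it is 0%.

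**7. Hospital, for scale only.** Under the SAP scheme (6,000 runs, 30% at the smaller hospital), a sex gap of 10 with an assumed hospital gap of 5 gave a type I error of 4.6% with both factors omitted. Power was 82%, against 84% with both included. The SAP claims no such hospital effect.

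**The case against.** The strongest reply is that the model part is a small matter. The estimate is unbiased, the test is conservative, and 37 per group gives 80.8% power with no covariates, so the design does not depend on adjusting for sex. For gaps up to 10 points the loss is at most about half a point on an interval 13.9 points wide. A 15-point gap is a full SD and 1.5 times the difference the trial is designed to detect, and nothing in the documents supports it. The figures also come from a single time point without baseline, whereas the plan is a mixed model over three visits with baseline ATRS.

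All of this stands as a limit on size. The larger losses should not drive the judgement, and the figures are illustrations, not predictions for the planned model. It does not remove the point. The plan stratifies on a factor it calls prognostic and then ignores it, and putting it in costs less than 0.1 point of power even if sex has no effect.

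On the allocation schemes, the SAP may simply be the later account: its reference list carries an access date in May 2023, against a protocol dated January 2021. But SAP section 7 describes the SAP as supplementing the protocol, and nothing says that it replaces protocol 16a.

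**Conclusion.** Both parts hold. The documents give two current and incompatible descriptions of the strata and block sizes. Under either one, the primary model omits at least one stratification factor: sex always, and hospital as well if the SAP scheme was used.

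The effect is a modest loss of precision in one direction. With 20% women, SD 15 and no baseline covariate, the interval is 0-4% wider than necessary for sex gaps of 0-10 points, and 9% wider at an unsupported 15 points. Baseline adjustment could reduce this, possibly to nothing. A hospital effect is possible, but the documents give no basis for sizing it. This should be corrected because correction is nearly free. The trial's validity does not depend on it.

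**What to change.** 1. Check the list generated for the trial. Correct protocol 16a or SAP 3.2 so that both give the strata and block sizes actually used, and say when and why the scheme changed if it did.
2. Before unblinding, amend the model sentence in protocol 20a and SAP 6.1 to read: *fixed effects for time, group allocation, baseline value and the stratification factor(s) used in the randomisation list*. That means sex in either case, and hospital if it was a stratum. Fixing this in advance also removes any later choice between adjusted and unadjusted results.

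**Cost.** One or two degrees of freedom out of about 74 patients, and no change to the 37 per group or the total of 82. Sex is already collected (SAP 2.3: "Descriptive data will be registered at baseline: age, sex, height, weight, body mass"). Hospital is not among the listed baseline items, so if it was a stratum it should be taken from the randomisation record. Protocol section 25 requires important modifications to be registered and approved by the ethics committee, and a change to the primary model may count as one.

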## 4. Study Population

Study participants will be included after the first visit to the emergency departments at Aalborg University Hospital and at North Denmark Regional Hospital Hjørring.

Inclusion criteria:

- Acute Achilles tendon rupture treated non-surgically.
- Diagnosed within 3 days of injury.
- Age 18-65 years and able and willing to participate in the intervention
- Able to speak and understand Danish.

Exclusion criteria:

- Achilles tendon rupture close to insertion on calcaneus or in the musculo-tendinous junction of the triceps surae.

- Previous Achilles tendon rupture or other conditions in either leg causing lower leg disability (pain, deficits in strength or range of movement).
- Treated with fluorquinolons or corticosteroids within the last 6 months.
- Diabetes or rheumatic diseases.
- Severe medical illness: ASA score higher than or equal to 3 (21).

Excluded patients and patients not willing to participate will follow the usual program of rehabilitation for non-surgical treatment at Aalborg University Hospital. They can participate in a separate cohort with the questionnaires at the same follow-up time points.

## **5. Data handling**

The data will be collected and stored in RedCap at Aalborg University Hospital. There will be a separate entry form in RedCap with questionnaires for the participants. A link to the questionnaires will be sent by email, and for follow-up it will also be available from a computer at each session.

## **6. Statistical Analysis**

The data analysis will be performed using the latest STATA version.

Information on screening, randomization and completing follow-up will be presented in a CONSORT flow diagram.

### ***6.1. Primary Endpoint***

Descriptive statistics (mean (standard deviation) or median (interquartile range) for continuous variable or frequencies and proportions for categorical variables) will be used to describe demographics, for the two treatment groups individually and overall sample.

The primary intention-to-treat analysis will investigate the between-group difference in ATRS. We will use a linear mixed effects regression model with the participant as random effect and time 13, 26 and 52 weeks, group allocation (standard care vs standard care plus add-on) and baseline value as fixed effects. Conclusions will only be drawn based on the primary endpoint (13 weeks). We will use Q-Q plots and histograms to assess data normality.

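### The primary mixed model as listed gives no 13-week group difference, and adding only a group-by-time term would leave that difference with a standard error pooled over three visits

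*SAP*

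**What the plan says.** SAP 6.1 (Primary Endpoint) sets out the primary analysis: "We will use a linear mixed effects regression model with the participant as random effect and time 13, 26 and 52 weeks", together with "group allocation (standard care vs standard care plus add-on) and baseline value as fixed effects". Protocol 20a has the same model, a "linear mixed effects regression model with the participant as random effect" and the same fixed effects. Neither document lists a group-by-time term.

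SAP 6.1 then confines inference to one visit: "Conclusions will only be drawn based on the primary endpoint (13 weeks").

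Neither document names a residual covariance structure, visit-specific variances, a robust standard error or a degrees-of-freedom method. The only model check planned concerns normality: "We will use Q-Q plots and histograms to assess data normality". SAP 6 names the software without commands or options: "The data analysis will be performed using the latest STATA version".

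SAP 3.1 bases the sample size on a "clinical relevant difference at 10 points and estimated standard deviation 15 point", with 5% two-sided alpha, 80% power and 37 per group. No SD is given for 26 or 52 weeks.

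**The concern.** The trial will draw one conclusion, from ATRS at 13 weeks. The model has to deliver that difference and a standard error that belongs to it. Two gaps stand in the way.

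First, with time, group and baseline as main effects only, the group coefficient is a single effect common to all three visits. If the benefit of early exercise fades as both groups recover, this coefficient understates the 13-week difference; if the benefit grows, it overstates it.

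Second, the obvious repair is to add group-by-time and change nothing else. A participant random intercept with independent, equal-variance residuals implies one total variance and one correlation for all visits, so the 13-week contrast borrows its variance from 26 and 52 weeks. ATRS is the sum of ten items scored 0 to 10, hence bounded, and patients are recovering between weeks 13 and 52. Equal spread at the three visits is an assumption that the plan neither states nor checks. If it fails, the nominal 5% level and 80% power may not hold for the only contrast that counts.

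**Working it through.** **Inputs.** From SAP 3.1: difference 10, SD 15, two-sided alpha 5%, power 80%, 37 per arm, 82 in total. SD 15 is taken as the 13-week SD because the calculation concerns the primary endpoint. SDs at 26 and 52 weeks and the within-person correlation are not in the documents; all values used below are assumptions. The closed forms take complete data and ignore the gain from baseline adjustment.

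**The plan's own figure.** The normal approximation gives 36 per arm. The noncentral t gives 37, with power 80.8%, which matches the plan. The sample size is not in dispute.

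**Step 1: what the listed model estimates.** With complete data, the common group effect is the plain average of the three visit effects. For assumed true effects of 10, 5 and 2 points this is (10 + 5 + 2)/3 = 5.67. Simulations gave 5.8 and about 5.65. The 13-week effect in that example is 10.

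The standard error of this averaged effect is sound even when visit SDs differ. With 37 per arm and correlation 0.5, the model and empirical standard errors were 3.34 and 3.36 for SDs 15/18/20, 2.52 and 2.53 for 15/13/12, and 2.34 and 2.34 for 15/12/10. Rejection under the null was 5.3% to 5.5%. So the written model has the wrong target, not a badly wrong standard error.

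**Step 2: group-by-time added, equal-variance residuals kept.** For the 13-week difference:

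- true SE = sqrt(2 × SD13² / n) = sqrt(2 × 225 / 37) = 3.49
- model SE = sqrt(2 × mean(SD13², SD26², SD52²) / n)
- ratio r = model SE / true SE
- true alpha = 2(1 − Φ(1.96 r))
- power = Φ(10/3.487 − 1.96 r), where 10/3.487 = 2.867

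For 15/18/20 the mean variance is (225 + 324 + 400)/3 = 316.3, so r = sqrt(316.3/225) = 1.186. Alpha is 2(1 − Φ(2.324)) = 2.0%, and power is Φ(2.867 − 2.324) = 70.7%.

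| Assumed SD at 13/26/52 weeks | Mean variance | Model SE | r | True alpha | Power |
|---|---|---|---|---|---|
| 15/15/15 | 225.0 | 3.49 | 1.000 | 5.0% | 81.8% |
| 15/18/20 | 316.3 | 4.14 | 1.186 | 2.0% | 70.7% |
| 15/16/17 | 256.7 | 3.73 | 1.068 | 3.6% | 78% |
| 15/14/13 | 196.7 | 3.26 | 0.935 | 6.7% | – |
| 15/13/12 | 179.3 | 3.11 | 0.893 | 8.0% | – |
| 15/12/10 | 156.3 | 2.91 | 0.834 | 10.2% | – |
| 15/18/12 | 231.0 | 3.53 | 1.013 | 4.7% | 81.1% |
| 15/18/11.2 | 224.8 | 3.49 | 1.000 | 5.0% | 81.8% |

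Power is left out where alpha is inflated, since it is not comparable there.

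**Step 3: check by simulation.** REML random-intercept fits with the interaction, 41 per arm, correlation 0.6 and 600 runs per case gave the same pattern. For 15/20/20 the model SE was 4.10 against an empirical 3.27, with 1.2% rejection under the null. For 15/10/10 it was 2.64 against 3.49, with 15% rejection (11.7% with 10% dropout). A cluster-robust standard error was about 3.3 in both cases.

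**Step 4: variance taken from the 13-week data.** The 13-week SE is then 3.49 at SD 15 whatever the later SDs. Simulated alpha was 4.9% to 5.0% and power about 81%.

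**The case against.** The strongest reply is that the alpha figures in Step 2 do not describe the plan as written. They appear only once a group-by-time term is added, and the listed model has none. Its common group effect keeps an alpha near 5%. This stands: a reader might infer that the current text carries an 8% or 10% false-positive rate, and the documents do not support that. The defect in the written model is that it averages over visits. The pooled variance matters because it would pass into the natural repair. That repair may even be what the authors have in mind, since they conclude at 13 weeks and SAP 2.2 speaks of comparing later changes between groups.

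Three narrower objections also stand.

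- A reader might infer that a participant random effect forces one variance on all visits. It does not. It can be combined with visit-specific residual variances or a robust standard error. Equal variance is the default reading of a text that leaves the structure open.
- A reader might infer that the standard error is wrong whenever the spread of ATRS changes. It is not. It is correct when the three variances average to the 13-week variance, as with 15/18/11.2, and almost correct for 15/18/12.
- A bounded score and recovery over time make unequal spread plausible but do not demonstrate it. The documents give one SD, so neither the size nor the direction of any error can be derived from them.

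What does not stand is that the choice can be left until analysis. It affects the error rate of the only contrast on which conclusions rest, and the planned normality plots are not a check of variance by visit.

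**Conclusion.** The point holds in two linked parts. The listed model does not produce the 13-week difference to which conclusions are confined; this follows from the text alone. Adding only a group-by-time term, with default equal-variance residuals, would produce that difference with a standard error that is right only if the mean of the three visit variances equals the 13-week variance.

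The size of the second part is conditional. With SD 15 at 13 weeks, 37 per arm, complete data and assumed later SDs, true alpha ranged from 2.0% (with power down to 71%) to 10.2%, with no error in a case such as 15/18/11.2. The random-intercept model therefore cannot be defended as reliably conservative, nor can it be called anti-conservative. The stated 37 per arm is reproduced and is unaffected.

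**What to change.** In SAP 6.1 and protocol 20a, replace the model sentence with a repeated-measures mixed model that has:

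- visit (13, 26, 52 weeks) as a category, with group, baseline value and group-by-visit terms, and preferably baseline-by-visit;
- an unstructured covariance over the three visits within participant;
- REML estimation with a small-sample degrees-of-freedom correction such as Kenward-Roger;
- the group difference at 13 weeks from this model named as the primary contrast.

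Visit-specific residual variances or a cluster-robust standard error would be acceptable alternatives to the unstructured covariance. Group-by-visit is needed in every case. Baseline-by-visit and the particular degrees-of-freedom method are good practice, but the pooled-variance problem can be corrected without them.

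The cost is a short change of wording in two places. The unstructured covariance has six parameters (three variances, three covariances) against two for the random intercept, so four more, which three visits and 82 participants can support. The critical value becomes slightly wider. No extra data, visits or participants are needed.
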